3.6.1 Adverse Events

The original terms recorded on the eCRF by the Investigators for adverse events will be standardized by the Sponsor. Adverse events will be summarized by mapped term and appropriate thesaurus level, including separate exploratory analyses of ATE events (Appendix 3).

Separate summaries will be prepared for systemic and ocular adverse events, with events in the study eye and non-study eye summarized separately. SAEs will be summarized similarly. Adverse events leading to discontinuation from the study will be listed and tabulated.

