3.1.1 Overview of the Study Design

[figure not shown]
The three groups of this study are as follows (see [Figure 1](#)):

- Arm A: 0.3 mg ranibizumab IVT
- Arm B: 1.5 mg RO6867461 IVT
- Arm C: 6 mg RO6867461 IVT

This study will consist of a treatment period (20 weeks) and an observational period (up to 16 weeks), for a total study length of up to 36 weeks. During the treatment period, the study drug will be administered to the patients on Day 1 and on every 4th week, for a total of 6 injections. During the observational period, patients will be evaluated every 4th week. If during any of these evaluations the patients meet the pre-specified criteria (see Section 4.3.1.1), the patients will receive a single dose of 0.3 mg ranibizumab, and exit the study. They will receive a follow up phone call 7 days after the dose of ranibizumab to evaluate any potential adverse events. Otherwise, patients will exit the study once they have completed the observational visit at week 36.

Only one eye will be selected as the study eye (see Section [4.3.1](#)).

Figure 1 Study Design

Q4W=every 4 weeks.

The total duration of the study for each patient will be up to 40 weeks, divided as follows (see [Figure 1](#)):

- Screening: *Up to 4 weeks*
- Baseline: *Day 1*
- Study treatment administration *period*: *From Day 1 to Week 20*
- *Observational period*: *From Week 20 up to Week 36*
- *Safety follow up call*: *During the observational period and 7 days after ranibizumab administration*

Patients will be admitted to the investigational site on Day 1 and for subsequent scheduled visits and will be discharged the same day after all mandatory and safety assessments, as specified in the Schedule of Assessments (SoA; see [Appendix 1](#)), are completed.

If a site has an unexpected issue (e.g., the interactive voice and web response system (IxRS) is not able to assign the study kit), the patient's study treatment may be administered within 3 working days of the scheduled treatment visit with the Medical Monitor's permission. The interval between two study treatment administrations needs to be at least 21 days.

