5.3.1 Adverse Event Reporting Period

Investigators will seek information on adverse events at each patient contact. All adverse events, whether reported by the patient or noted by study personnel, will be recorded in the patient's medical record. Adverse events will then be reported on the Adverse Event eCRF as follows:

After informed consent has been obtained but prior to initiation of study drug, only serious adverse events caused by a protocol-mandated intervention should be reported (e.g., serious adverse events related to invasive procedures such as angiographies). Any other adverse event should not be reported.

RO6867461—F. Hoffmann-La Roche Ltd
64/Protocol BP30099, Version 3

After initiation of study drug through the final visit, all adverse events, regardless of relationship to study drug, will be reported.

After the final visit and/or subsequent follow-up phone call, as applicable, investigators should report any deaths, serious adverse events, or other adverse events of concern that are believed to be related to prior treatment with study drug (see Section 5.6)

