6. STATISTICAL CONSIDERATIONS AND ANALYSIS PLAN

6.1 DETERMINATION OF SAMPLE SIZE

The sample size is based on the primary efficacy outcome of mean change in BCVA from baseline at Week 24 in the *treatment-naïve patients*. Each RO6867461 dose (Arms B and C) will be compared with the control group (Arm A).

Consider 50 *treatment-naïve* patients randomized to Arms A, B, and C, with a drop-out rate of 10%. Assuming a standard deviation of 11 letters, this sample size provides 80% power to detect a true difference of 5 letters at the one-sided α level of 10%. The minimum detectable difference is approximately 3 letters.

Approximately 60 previously IVT anti-VEGF treated patients will be enrolled in addition for exploratory analyses.

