2.1 RANDOMIZATION

After written informed consent has been obtained, all patients will receive a screening number assigned through the Interactive Voice and Web Response System (IxRS). After all patient eligibility requirements are confirmed on Day 1 visit the site personnel will contact the IxRS for assignment of a patient identification number (a separate number from the screening number).

Approximately 50 treatment-naïve patients will be randomized on each arm (1:1:1 randomization scheme) and approximately 30 patients previously treated with IVT anti-VEGF will be randomized into arms A and C. Randomization will be stratified for the three factors below:

- Baseline BCVA ETDRS letter score assessed on Day 1 (64 letters or better vs. 63 letters or worse)
- Previous Macular Laser treatment (Yes/No)

Previous IVT anti-VEGF treatment in study eye (Yes/No)

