The primary efficacy variable is the study eye BCVA change from baseline at Week 24. The primary efficacy analysis will be performed using a Linear Mixed Effects Model for Repeated Measurements (MMRM) model. The model will include the categorical covariates of treatment group, categorical visit, and visit by treatment group interaction term, randomization stratification factors, and a continuous covariate of baseline BCVA. An unstructured covariance will be used to account for within-patient correlation (General Linear Model), but another variance-covariance structure such as AR(1) + random patient effect may be selected in case of convergence issues. The primary statistical test will aim to test the null hypothesis:

H_0 : There is no difference between either of the RO6867461 arms (Arms B and C) and the control group (Arm A) for mean BCVA change from baseline at Week 24 in the treatment-naïve patient population vs.

H_A : Arm B or C is different from arm A.

The model-based estimate of the difference between each of the treatment groups (Arms B and C) and the control group (Arm A) at Week 24, together with 80% confidence interval and corresponding p-value will be reported as the primary

efficacy measures. The mean and 80% CI within each treatment group and for the difference between RO6867461 treatment groups (Arms B and C) and the control group (Arm A) at the other time points will also be reported. There will be no formal correction for multiple comparisons. Tests for arms B vs A and C vs A will be carried out at one-sided 10% alpha.

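### After Week 24 adverse-event follow-up depends on loss of effect, and the SAP text plans no common-window or exposure-adjusted summary

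*SAP*

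**What the plan says.** - **Collection period.** Protocol 5.3.1 has adverse events reported as follows: "After initiation of study drug through the final visit, all adverse events", whatever their relation to study drug. The window therefore ends at the patient's own last visit, with a follow-up call where applicable.
- **Exit rule.** All arms receive six injections from Day 1 to Week 20. At the four-weekly evaluations after that, if the criteria in Protocol 4.3.1.1 are met, "the patients will receive a single dose of 0.3 mg ranibizumab, and exit the study" (Protocol 3.1.1). Both a CST increase of at least 50 µm and a BCVA loss of at least 5 letters due to DME are required. The first such comparison is at Week 24. Patients who exit this way are called 7 days later about adverse events; the others stay to Week 36.
- **Durability.** Exploring duration of effect is a secondary objective (Protocol 2.2), and SAP 1.2.4 lists time to observational ranibizumab as an outcome. The amendment history (item 5) says the design was changed so that durability could be compared between RO6867461 and ranibizumab.
- **Safety summary.** SAP 1.2.1 names incidence and severity of ocular and non-ocular events. SAP 3.6.1 adds: "Adverse events will be summarized by mapped term and appropriate thesaurus level, including separate exploratory analyses of ATE events". SAP 3.6.8 summarises dosing duration and the share of planned injections given, not time under observation. SAP 3.6 refers to the LoPO for the full list of safety reports.

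**The concern.** Length of adverse-event follow-up after Week 24 is itself an outcome of treatment. If one arm holds its effect longer, its patients are watched longer and have more time to record an event, even when the underlying rates are equal. The exposure summary in SAP 3.6.8 would not show this, because dosing ends at Week 20 in every arm.

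Safety is a secondary objective. Protocol 5.7 also has the internal monitoring committee follow event incidence, and sends clinically relevant imbalances that do not favour the test product to health authorities. An imbalance that comes only from longer observation should not enter that process unrecognised.

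A second gap sits beside the first. The SAP text has no rule for events that start after the observational ranibizumab injection, so in Arms B and C these would mix with events that follow RO6867461 alone.

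**Working it through.** **The plan's own figures.** The plan gives no figure for adverse events. Its sample-size statement can be reproduced and fixes the arm sizes. Protocol 6.1 says the design "provides 80% power to detect a true difference of 5 letters at the one-sided α level of 10" per cent, "Assuming a standard deviation of 11 letters". With 50 per arm and 10% drop-out, 45 are evaluable: power = Φ(5 / (11·√(2/45)) − 1.2816) = Φ(2.156 − 1.282) = 80.9%, which agrees. Adding about 30 previously treated patients to each of Arms A and C (SAP 2.1), the safety set is about 80 in A, 50 in B and 80 in C.

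**Assumptions.** The documents give no adverse-event or exit rates by arm, so the following are assumed ranges:
- the same constant hazard λ in both arms, with λ = −ln(1 − r)/24 for an event with 24-week risk r;
- exits at Weeks 24, 28, 32 or 36, each followed by one more week to the call; otherwise follow-up of 36 weeks; no other drop-out;
- exit probability at Week 24, then at each of Weeks 28 to 36 among those remaining, as in the table.

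**Formulas.** Mean follow-up = Σ P(exit at t)·(t + 1) + P(no exit)·36. Incidence = Σ P(follow-up = u)·(1 − e^(−λu)).

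Example, large scenario, less durable arm: 0.10×25 + 0.45×29 + 0.225×33 + 0.1125×37 + 0.1125×36 = 31.2 weeks. More durable arm: 0.02×25 + 0.098×29 + 0.0882×33 + 0.0794×37 + 0.7144×36 = 34.9 weeks. Ratio 1.12.

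| Scenario (less vs more durable arm) | Exit at Wk 24 | Exit per visit, Wk 28–36 | Mean weeks | Ratio | Event with r = 10% | Event with r = 30% |
|---|---|---|---|---|---|---|
| Mild | 5% vs 5% | 15% vs 10% | 34.2 vs 34.6 | 1.01 | 13.9% vs 14.1% | 39.8% vs 40.1% |
| Moderate | 5% vs 5% | 30% vs 15% | 33.0 vs 34.2 | 1.04 | 13.5% vs 13.9% | 38.7% vs 39.8% |
| Large | 10% vs 2% | 50% vs 10% | 31.2 vs 34.9 | 1.12 | 12.8% vs 14.2% | 37.0% vs 40.4% |
| Extreme | 100% vs 0% | none left vs 0% | 25 vs 36 | 1.44 | 10.4% vs 14.6% | 31.0% vs 41.4% |

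The follow-up ratio is what a rare event would show. For r = 10% the incidence ratios are slightly smaller: 1.01, 1.03, 1.11 and 1.41.

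**Against sampling error.** With 80 per arm the standard error of the difference is about 5 points (r = 10%) to 8 points (r = 30%). In the large scenario the gap is 1.4/5.4 = 0.26 SE and 3.4/7.7 = 0.44 SE. In the extreme case it is 4.2/5.2 = 0.8 SE and 10.4/7.6 = 1.4 SE. Only for a very common event (r = 60%) does the large scenario pass one half: 4.2/7.1 = 0.59 SE.

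**Injection-related study-eye events.** Let q be the risk per injection and e the share of an arm that exits with ranibizumab. Incidence is 1 − (1 − q)^6·(1 − e·q), so the less durable arm is higher by (1 − q)^6·q·(difference in e). For q = 2% to 5%, also assumed:
- moderate (e = 0.67 vs 0.42): 0.5 to 0.9 points;
- large (0.89 vs 0.29): 1.1 to 2.2 points;
- extreme (1 vs 0): 1.8 to 3.7 points.

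This runs opposite to the follow-up effect.

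**After the fix.** No loss-of-effect exit precedes the Week 24 visit. Under equal hazards, Day 1 to Week 24 incidence has an expected ratio of 1.00 in every scenario, and so do rates per patient-year.

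**The case against.** The strongest reply is that this matters little. Dosing is the same in all arms to Week 20, so the first 24 weeks are comparable by design apart from ordinary drop-out. The event summaries are descriptive, the ATE analysis is labelled exploratory, and SAP 3.8 calls the study hypothesis-generating. Exit needs both an anatomical and a visual criterion, so wide gaps in follow-up need high exit rates. All of this stands, and it limits the severity.

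Some stronger readings are tempting, and the documents do not support them:
- **That SAP 3.6.1 prescribes crude incidence.** It names no statistic or denominator. The text is silent on person-time, and the LoPO might contain more. A choice of window and an attribution rule still belong in the SAP itself.
- **That durability is expected to differ.** The amendment rationale is to evaluate whether it does. Without a difference this bias does not arise.
- **That follow-up differs by something like 28 versus 34 weeks.** With a constant hazard, 34.0% would then become 39.6%. But even half of the remaining patients leaving at every visit from Week 28 gives a mean of 31.2 weeks in the large scenario.

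Patient-year rates also have a weakness. They add time off study drug to the more durable arm's denominator, which dilutes its injection-related ocular rates. That objection is sound, and the fix limits those rates to non-ocular events and ATE.

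**Conclusion.** The gap is real, and its effect is conditional. If durability differs by arm, whole-study incidence by term is not a like-for-like comparison, and nothing in the protocol or SAP text corrects for it. For time-driven events the more durable arm is inflated by a ratio of about 1.01 to 1.12 over the assumed exit rates, and about 1.44 when all patients in one arm exit at Week 24 and none in the other. For 24-week risks up to 30%, the distortion short of that extreme is under 0.5 SE.

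A reader might infer that a more durable drug will simply look less safe, with ocular inflammation moving the same way as ATE. That does not follow. For injection-related study-eye events the extra ranibizumab injection and the 7-day call can raise the less durable arm instead.

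The sizes rest on equal constant hazards and on exit and event rates that are not in the documents. Severity is minor to moderate.

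**What to change.** In SAP 3.6.1:
1. Make incidence of adverse events, SAEs and ATE from Day 1 to the Week 24 visit, before any observational ranibizumab, the main between-arm summary.
2. Keep the whole-study tables. Add observation time by arm, and rates per patient-year for non-ocular adverse events and ATE.
3. Tabulate separately the events that start after observational ranibizumab, by randomised arm.

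If the LoPO already lists such tables, state the window and the attribution rule in the SAP text and refer to them.

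The cost is a few more tables from data already collected, with no change to study conduct. The drawback is that late events appear only in the supporting whole-study tables, so the report should point to them.

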1.2.1 Previous Non-Clinical Studies

Pharmacological studies were performed in vitro and in vivo to investigate the target binding affinity, specificity, and biological activity of RO6867461. In vitro studies demonstrated that RO6867461 binds the target molecules VEGF and Ang-2 with high affinity. Mutations in the Fc region of RO6867461 abolish binding to Fc_Y receptors, located on effector cells, and the neonatal Fc receptor (FcRn).

In the absence of a suitable model of DME, pharmacological evaluation in vivo focused on well characterized models of choroidal vessel edema and neovascularization. These evaluations demonstrated that RO6867461 reduces the formation of neovessels, the leakiness of existing CNV lesions, and subsequent injury to the retina due to lesion formation in a mutant mouse model of early bilateral CNV and a laser-induced model of CNV in cynomolgus monkeys (*RO6867461 Investigator's Brochure* Version 4).

RO6867461—F. Hoffmann-La Roche Ltd
22/Protocol BP30099, Version 3

In a 2-month Good Laboratory Practice (GLP) study in cynomolgus monkeys, ocular and extra-ocular findings occurred following three IVT injections of the highest 3 and 6 mg/eye/dose. The no observed adverse effect level (NOAEL) was established at a dose of 1.5 mg/eye/dose for IVT administration.

In a 6-month GLP study in cynomolgus monkeys, no changes were observed following seven IVT injections every 4 weeks at the low dose of 0.5 mg/eye/dose comprising the NOAEL. Dose-dependent ocular inflammatory cell infiltration and clinical signs of ocular inflammation occurred in RO6867461-treated eyes at 1.5 or 1.5/3 mg/eye/dose IVT following the same dosing schedule.

In both studies, findings generally correlated with the systemic presence of anti-drug antibodies (ADAs) against RO6867461 and exposure loss in the serum of animals. In addition, immunohistochemistry confirmed the presence of immune-complex deposits in RO6867461-treated animals with ocular and extra-ocular findings (in the 3-month study). Therefore, these effects were consistent with an immune-mediated response to a humanized antibody like RO6867461 in non-human primates.

RO6867461 did not induce any neurological (CNS) findings or effects on heart rate/electrocardiogram endpoints (including QT and QTc [corrected QT interval]), respiratory rate, or body temperature in cynomolgus monkeys up to 6 months treatment.

See the [RO6867461 Investigator's Brochure](#) for details on nonclinical studies.

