5.3.5 Procedures for Recording Adverse Events

Investigators should use correct medical terminology/concepts when recording adverse events on the Adverse Event eCRF. Avoid colloquialisms and abbreviations.

For the purposes of reporting events of infection and inflammation of the eye, the following terms and definitions should be used.

- **Iritis:** the presence of inflammatory cells in the anterior chamber
The presence of aqueous flare alone will not constitute iritis but should be documented as an anterior chamber flare for adverse event reporting purposes.
- **Iridocyclitis:** the presence of inflammatory cells in both the aqueous and vitreous
- **Vitritis:** the presence of active inflammation in the vitreous, demonstrated by the presence of inflammatory cells (trace or greater)
Active inflammation in the vitreous should be clinically differentiated from cellular debris from prior episodes of inflammation, hemorrhage, or other causes.
- **Endophthalmitis:** diffuse intraocular inflammation predominantly involving the vitreous cavity but also involving the anterior chamber, implying a suspected underlying infectious cause

Note: Trace benign, aqueous pigmented cells visible on slit-lamp examination that are caused by dilation and are not RBCs or WBCs or the result of any ocular disorder should not be recorded as an adverse event. Only one adverse event term should be recorded in the event field on the Adverse Event eCRF.

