1.2 OUTCOME MEASURES

1.2.1 Safety Outcome Measures

The safety outcome measures for this study are as follows:

- Any relevant safety observations derived from BCVA (modified ETDRS charts), slit-lamp examination, dilated binocular indirect high-magnification ophthalmoscopy, intraocular pressure (IOP), fundus photography (FP), SD-OCT, and angiography
- Incidence and severity of ocular adverse events
- Incidence and severity of non-ocular adverse events
- Incidence of laboratory abnormalities, based on hematology, clinical chemistry, and urinalysis test results
- Incidence of anti-RO6867461 antibodies
- ECGs
- Vital signs

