3.6 SAFETY ANALYSES

All safety analyses will be based on the safety analysis population. The LoPO contains the full list of reports for safety analyses.

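### The SAP text specifies no pooled count of study-eye intraocular inflammation and no severity summary for ocular adverse events

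*SAP*

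**What the plan says.** **Collection.** Protocol 5.3.5 sets the vocabulary: "For the purposes of reporting events of infection and inflammation of the eye, the following terms and definitions should be used". The terms are iritis, iridocyclitis, vitritis and endophthalmitis, with anterior chamber flare recorded under its own name when it occurs alone. Each event field takes one term. Protocol 5.3 and 5.3.3 require a severity rating for every adverse event.

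**Outcome.** SAP 1.2.1 lists "Incidence and severity of ocular adverse events" among the safety outcome measures, as does Protocol 3.3.1.

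**Analysis.** SAP 3.6.1: "Adverse events will be summarized by mapped term and appropriate thesaurus level, including separate exploratory analyses of ATE events (Appendix 3"). It continues: "Separate summaries will be prepared for systemic and ocular adverse events, with events in the study eye and non-study eye summarized separately". Serious events are handled the same way. Appendix 3 gives the term list for ATE. SAP 3.6 adds: "The LoPO contains the full list of reports for safety analyses". The LoPO (List of Planned Outputs) is not among the documents.

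**Slit lamp.** Protocol 6.6.6 plans a tabulation, by grade, of intraocular inflammation seen at the slit-lamp examination. SAP 3.6.6 names only BCVA and IOP.

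**Animal data.** Protocol 1.2.1, on the 6-month monkey study: "Dose-dependent ocular inflammatory cell infiltration and clinical signs of ocular inflammation occurred in RO6867461-treated eyes at 1.5 or 1.5/3 mg/eye/dose IVT". It then comments that "these effects were consistent with an immune-mediated response to a humanized antibody like RO6867461 in non-human primates".

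**The concern.** Intraocular inflammation is one clinical idea that the trial records under at least four names. Protocol 6.6.6 treats it as one concept, and severe intraocular inflammation is a criterion in Protocol 4.7.1.1 (stopping study drug) and 5.1.4 (sight-threatening events). The SAP's adverse event section does not put the names back together.

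With about 80 patients in an arm and an uncommon event, each row may hold only one or two patients. A real difference between 6 mg and ranibizumab could then look like scattered single events. The question a safety reader asks first is how many patients per arm had any inflammation in the study eye, and how bad it was. No analysis in the SAP text is specified to answer it. The animal finding makes inflammation a reasonable event to define in advance.

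**Working it through.** The documents give no figure on this point to reproduce, and no human inflammation rate for this trial. The check has two parts.

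**1. Is inflammation pooled anywhere in the SAP text?**

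- *Adverse event data:* Protocol 5.3.5 splits inflammation into several terms. SAP 3.6.1 summarizes by mapped term and by a thesaurus level that it does not name. The only custom group is ATE.
- *Severity:* a named outcome in SAP 1.2.1, collected under Protocol 5.3.3. Neither SAP 3.6.1 nor Protocol 6.6.1 mentions a severity summary.
- *Slit-lamp data:* the grade table is in Protocol 6.6.6 and absent from SAP 3.6.6.

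The SAP text therefore pools inflammation from neither source. The slit-lamp gap and the severity gap need no assumed rates.

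**2. What does splitting cost?**

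From the documents:
- Treatment-naïve: 150/3 = 50 per arm. Previously treated: 60 randomized 1:1 to Arms A and C, so 30 each.
- The safety population is all dosed patients (SAP 3.1.1): about 50 + 30 = 80 in each of Arms A and C, and 50 in Arm B.

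Assumed:
- Patients with any study-eye inflammation: 2% in Arm A; 10% or 5% in Arm C.
- Four terms, at most one per affected patient, split evenly (25% each) or unevenly (60/20/10/10).
- A visible excess means at least 4 more patients in Arm C than in Arm A.

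Pooled count, with X_C ~ Bin(80, p_C) and X_A ~ Bin(80, p_A):

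P(X_C − X_A ≥ 4) = Σ_a P(X_A = a) · P(X_C ≥ a + 4)

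Single rows, with multinomial counts over the four terms (400,000 simulated trials): P(max over terms of (C_k − A_k) ≥ 4).

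Expected patients at 10% versus 2%: 80 × 0.10 = 8.0 and 80 × 0.02 = 1.6 pooled. With an even split these become 2.0 and 0.4 per row.

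| Arm C vs Arm A, 80 each | Pooled | Any row, even split | Any row, 60/20/10/10 |
|---|---|---|---|
| 10% vs 2% | 84% | 37% | 58% |
| 5% vs 2% | 31% | 5% | 13% |

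The same sum with p_C = p_A = 2% gives about 2.4%, so a 4-patient pooled excess would seldom arise by chance at that rate.

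A second yardstick points the same way: a one-sided Fisher test at 10%, 80 per arm, even four-way split. At 10% versus 2%, power is 72% pooled, against 10% for a given row and about 34% for any row (treating rows as independent). At 8% versus 2% it is 53%, 5% and about 20%.

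**The case against.** Several points on the other side are sound.

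- **Thesaurus level.** A reader might infer that events are counted only term by term. SAP 3.6.1 does not say that: it also promises an appropriate higher level. What remains is that the level is not named and need not coincide with an inflammation group.
- **The LoPO.** A reader might infer that the trial will never report a pooled count or a severity table. That cannot be concluded, because SAP 3.6 places the full list of safety reports in the LoPO. The point is limited to the SAP text. Even so, the SAP defined the ATE group in its own appendix.
- **Slit-lamp data.** The protocol does plan inflammation by grade. But the SAP drops that table, so this source does not close the gap there.
- **Severe cases.** Inflammation graded 4+ is sight-threatening and serious under Protocol 5.1.4, and the SAP summarizes serious events by eye. This covers the worst cases, not mild or moderate ones, where a dose-related pattern might first show.
- **The animal finding.** A reader might infer an established human harm of the drug. The documents do not support that. Protocol 1.2.1 reads the finding as a primate immune response to a humanized antibody, Protocol 1.3 sees no need for warnings beyond those for other anti-VEGF agents, and Protocol 5.2 reports no safety signal in patients so far.
- **Rows can be read together.** Ocular events in the study eye are listed together, so a reader could add rows. But the sum can count one patient twice, and choosing the rows after seeing the data is what a prior definition avoids.
- **Assumed rates.** The even split is harsh, since it gives a quarter of events to endophthalmitis, which the protocol ties to suspected infection. The uneven split narrows the contrast but does not remove it. At 5% versus 2%, even the pooled count usually misses the excess.

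**Conclusion.** The point holds for the SAP text. It defines no grouped intraocular inflammation event, specifies no severity summary for a named severity outcome, and omits a protocol-planned table of inflammation by slit-lamp grade. The last two are plain mismatches within and between the documents. The first is a choice of counting rule where a better one is available at little cost.

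The size is illustrative. At 80 per arm, pooling raises the chance of a visible excess from 37–58% to 84% (10% versus 2%), or from 5–13% to 31% (5% versus 2%). This rests on assumed rates, an assumed split over four terms and an assumed 4-patient threshold. The direction does not depend on them: any division over rows weakens the view of a common excess.

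No efficacy conclusion is affected, and the raw data remain available for later tabulation. The change is worth making before unmasking, and would be unnecessary if the LoPO already lists these outputs.

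**What to change.** In SAP 3.6.1 add wording such as: *Intraocular inflammation in the study eye is a grouped event (iritis, iridocyclitis, vitritis, uveitis, anterior chamber cells or flare, endophthalmitis), with its preferred terms listed in an appendix as for ATE. The number and percentage of patients with at least one event will be shown by arm and by worst severity, with and without endophthalmitis. Ocular adverse events overall will also be tabulated by worst severity.*

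In SAP 3.6.6 restore the Protocol 6.6.6 table of slit-lamp inflammation by grade. It is not a duplicate: the grade describes the examination finding, whereas adverse event severity in Protocol 5.3.3 describes disruption of daily activity.

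If the LoPO already contains these outputs, a cross-reference from SAP 3.6.1 and 3.6.6 is enough.

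Cost: two short SAP edits, one preferred-term list and a few tables. The adverse events, their severity and the slit-lamp findings are already collected. Small downside: the group mixes terms of different clinical weight, which is why endophthalmitis is also shown separately.
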